### 5.4 Preparation and Administration of IP

The request for the IP will be sent to the research or general pharmacy associated with the nursing home and individually prepared for each subject.

If a subject becomes hospitalized, the research staff will contact the hospital staff to determine the feasibility of the IP being administered in the hospital.

### 5.5 Subject Compliance Monitoring

Patient adherence to study treatment will be monitored by study and/ or nursing home staff (or hospital staff) when they administer the IP.

# 5.6 Prior and Concomitant Therapy

Drugs listed as part of the exclusion criteria are not permitted during each of the two 2 days courses of treatment with Fisetin (Days 0 & 1 and Days 8 & 0). If patients are required to initiate these medications within these periods, then they will be removed from the study primarily due to risk of drug-drug interaction.

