### **4.4.2.** Treatment Discontinuation:

A subject's treatment may be discontinued prior to that subject completing the 4 days of drug treatment. Subjects whose treatment has been discontinued will remain in the study and, if feasible, will continue to be assessed for all planned efficacy and safety endpoints and will be included in statistical analyses. Some reasons may include:

- Subject safety issues
- Failure of subject or staff to adhere to protocol requirements
- Subject voluntarily withdraws from treatment
- Subject is unable to tolerate continued IP administration
- Subject experiences a Grade 3 or higher adverse event attributed to the IP by the investigator
- Subject experiences a Grade 3 or higher clinically significant laboratory abnormality attributed to the IP by the investigator
- Treating physician determines that continuing study treatment would not be in the subject's best interest
- Subject becomes lost to follow-up
- The investigator or the subject's nursing home attending physician, physician's assistant, or nurse-practitioner may discontinue a subject's treatment (without regard to the subject's or their LAR's consent) if they believe that continued treatment would be contrary to the best interests of the patient.

If premature treatment discontinuation occurs for any reason, the reason for premature treatment discontinuation, along with who made the decision (subject, LAR, responsible nursing home physician, physician's assistant, nurse-practitioner, investigator) will be recorded in the CRF.

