# 4.4.3. Subject Withdrawal:

A subject may be withdrawn from the study prior to that subject's completing all of the study related procedures if the subject or LAR decides to withdraw from the study (withdrawal of consent). Withdrawn subjects may not reenter the study.

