# 4.4.4. Premature Withdrawal from Study:

Subjects or their LAR may voluntarily withdraw from the study for any reason at any time. Subjects are considered withdrawn if they or their LAR state an intention to withdraw further participation in all components of the study or if subjects die. If premature withdrawal occurs for any reason, the reason for premature withdrawal from the study, along with who made the decision (subject, LAR, responsible nursing home physician, physician's assistant, or nurse-practitioner, investigator) will be recorded in the CRF.

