### 4.5. Data Collection and Follow-Up for Withdrawn Subjects

- For withdrawn subjects (due to withdrawal of consent) not undergoing any study intervention, no additional follow-up will be done.
- For withdrawn subjects (due to withdrawal of consent) receiving Fisetin (Intervention), any additional evaluation will be for subject safety only. Research data will not be collected on subjects after withdrawal of consent.

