### 5.2.3. Standard of Care

Subjects will continue to receive institutional standard of care for the treatment of COVID-19 pneumonia and other conditions. The use glucocorticoids, Hydroxychloroquine, Azithromycin, Remdesivir, or Metformin is permitted. Subjects administered Rapamycin or other mTOR inhibitors, should they become standard of care, will be withdrawn unless the Rapamycin or other mTOR inhibitors are held for ≥5 days before the first dose of Fisetin on Day 0 until 1 hour after the final Fisetin dose on Day 9. Subjects started on other treatments for COVID-19 will continue to be followed if possible until the end of the study.

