#### 8.2 Statistical Methods

All participants who are randomized will be included in the primary efficacy analysis. The analysis will follow the ITT principle (*i.e.* according to the treatment arm they are randomized to). For the primary analysis using the values of the 7-point scale, we will test the coefficient of the treatment effect (as a fixed effect) in an ordinal logistic regression model using a 2-sided 0.05 level Wald test after adjusting for key baseline variables such as baseline COVID severity status, age, and sex that show imbalance between the groups. Subjects who withdraw early but received at least some treatment will have their last known values carried forward until they complete the study at Day 180±14. All participants who receive any dose of drug (Fisetin or placebo) will be included in the safety and tolerability evaluation. The definitions of adverse events are described in Sections 9.1-9.3. Participants will be assessed over the entire period of drug administration. Frequency tables will be generated to summarize the occurrence of AE's by treatment arm. Comparisons of the rates of individual AEs will be done using tests of proportions such as the Fisher's exact test or Chi-squared test.

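### Sections 5.6 and 5.2.3 take participants out of the study where section 4.4.2 would only stop study drug, so an observable Day 14 score could be replaced by an earlier one

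*Combined protocol and SAP*

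**What the plan says.** **Rules that take participants out.** Section 5.6 bars the excluded drugs during the two dosing courses, Days 0-1 and 8-9 (the second day of the second course is misprinted there as 0). It continues: "If patients are required to initiate these medications within these periods, then they will be removed from the study". The main reason given is interaction risk. Section 5.2.3 adds: "Subjects administered Rapamycin or other mTOR inhibitors, should they become standard of care, will be withdrawn". That applies unless the drug is held from at least 5 days before Day 0 until 1 hour after the last dose.

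**Rules that keep participants in.** Section 4.4.2 says: "Subjects whose treatment has been discontinued will remain in the study". They are assessed for efficacy and safety where feasible and are analysed; safety issues are among its example reasons for stopping. Section 5.2.3 also says: "Subjects started on other treatments for COVID-19 will continue to be followed if possible until the end of the study". Section 3.1 keeps participants who start Remdesivir.

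**Withdrawal and analysis.** Section 4.4.3 ties withdrawal to a decision by the participant or representative. Section 4.4.4 covers those who "state an intention to withdraw further participation in all components of the study or if subjects die". It also has the decision-maker recorded, and the possible decision-makers include the nursing home clinician and the investigator. Section 4.5 says: "Research data will not be collected on subjects after withdrawal of consent". Section 8.2 analyses all randomized participants by intention to treat and adds: "Subjects who withdraw early but received at least some treatment will have their last known values carried forward".

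**The concern.** A participant who must start an interacting drug on Day 1 or Day 8 fits two rules. Under 4.4.2, with safety as the reason, study drug stops and the Day 14 score is still collected. Under 5.6 the participant leaves the study. The protocol does not define removal or say which rule prevails.

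Both trigger windows close before Day 14, the primary time point. If a site follows 5.6 literally, the Day 14 score may never be recorded, and the last earlier score may be carried forward in its place. Needing a new drug may be a sign of deterioration, so that earlier score could be better than the true one. Sites following different sections could also record different data for the same clinical course. Those removed for interaction risk are people whose safety follow-up should continue, and a score that was never collected cannot be recovered at analysis.

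**Working it through.** **1. The texts side by side**

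| Question | Sections that bear on it | Answer for a participant removed under 5.6 |
|---|---|---|
| Do they stay in the study? | 5.6: no. 4.4.2: yes, if seen as stopping study drug | Conflict |
| Is the Day 14 score collected? | 6.4 and 7.3 schedule it generally; 4.4.1 follows subjects wherever they are to Day 180 or death; 4.5 stops research data only after consent is withdrawn | Leans yes, not stated |
| Does safety follow-up continue? | Section 9 and 9.1.4: adverse events for all subjects to Day 180 | Leans yes, not stated |
| Which value is analysed? | 8.2: intention to treat, last value carried forward for early withdrawals who had some study drug | Carry-forward may well apply, since 4.4.4 envisages withdrawal decided by a clinician or investigator |

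**2. The plan's power figure**

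Inputs from 8.1: 75 per arm, two-sided 0.05, controls spread equally over 7 levels, log odds ratio 0.81. Levels are numbered in the order of section 2.1, so 1 is best and 7 is death.

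- Fisetin cumulative odds = control cumulative odds × e^0.81. Levels 1 to 7 become 27.3, 20.1, 15.4, 12.2, 9.9, 8.2 and 6.9%.
- V = (150/12) × (1 − Σp̄³), with p̄ the average of the two arms. Σp̄³ = 0.0240, so V = 12.5 × 0.976 = 12.20.
- Power = Φ(0.81 × √12.20 − 1.96) = Φ(2.829 − 1.96) = 80.8%.
- Sample size = 6 × (1.960 + 0.842)² / (0.81² × 0.976) = 73.5, so 74 per arm.

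The stated 80% with 75 per arm reproduces.

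**3. Effect of removal**

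The documents give no removal rate, and the trigger drugs are listed in the Investigator Brochure. Assumptions: a fraction x of participants who would be at levels 3 to 6 on Day 14 is removed, equally in both arms. Deaths stay at level 7. The carried score is k levels better, with level 1 the floor.

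Levels 3 to 6 hold 57.1% of controls and 45.8% of the Fisetin arm. Removed per arm:

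- x = 2%: 75 × 0.571 × 0.02 = 0.86 control; 75 × 0.458 × 0.02 = 0.69 Fisetin.
- x = 5%: 2.14 control and 1.72 Fisetin.

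Refitting the proportional-odds model to the shifted proportions and recomputing V gives:

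| x | Handling | Odds ratio | Power |
|---|---|---|---|
| 0 | all observed | 2.248 | 80.8% |
| 2% | carried, k = 1 | 2.246 | 80.7% |
| 2% | carried, k = 2 | 2.238 | 80.3% |
| 2% | carried, k = 3 | 2.228 | 79.9% |
| 5% | carried, k = 1 | 2.243 | 80.5% |
| 5% | carried, k = 2 | 2.223 | 79.6% |
| 5% | carried, k = 3 | 2.198 | 78.5% |
| 2% | left out | 2.253 | 80.6% |
| 5% | left out | 2.261 | 80.3% |

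For the worst row, log odds ratio = 0.788 and V = 12.18, so power = Φ(0.788 × √12.18 − 1.96) = Φ(0.789) = 78.5%. The rows for participants left out use V = n₁n₂/(3N) × (1 − Σp̄³) with the reduced arm sizes.

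**The case against.** The strongest reply is that the rest of the protocol already settles this. Someone removed under 5.6 has not withdrawn consent, so 4.5 does not stop data collection. Section 4.4.1 continues follow-up, and Section 9 continues adverse event reporting. If removal counts as an early withdrawal, 8.2 supplies a value. The trigger is also narrow. Exclusion 17 lets listed drugs be held around dosing, so 5.6 bites mainly when a listed drug must be started within a two-day window and cannot wait. The mTOR rule is conditional on those drugs becoming standard of care and not being held. Most COVID-19 drugs are permitted.

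Much of this stands. A reader might infer that removed participants drop out of the analysis, that their safety follow-up ends, or that no section bears on their follow-up. The documents support none of these: 8.2 includes all randomized participants, and 4.4.1, 4.5 and Section 9 all point towards continued follow-up. A reader might also infer that every mTOR inhibitor user is withdrawn, but 5.2.3 does not say that.

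The reply does not remove the conflict. The default sections are general, while 5.6 is specific and says the participant leaves the study. Carry-forward supplies a number, but an earlier one, where 4.4.2 would have the real one collected.

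**Conclusion.** The conflict is real and the consequence is minor. As written, 5.6 and the mTOR rule in 5.2.3 contradict 4.4.2 and sit badly with intention to treat. Following 5.6 literally can replace an observable Day 14 score with an earlier one after an event that may reflect worsening.

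Under the assumed 2% to 5% removal at levels 3 to 6, about 1 to 2 people per arm are affected. The odds ratio moves from 2.25 to no lower than 2.20, and power from 80.8% to no lower than 78.5%. If those participants are left out instead, power is 80.6% to 80.3%. These figures rest on the assumed rate, on equal removal in both arms at a given level, on a carried score 1 to 3 levels better, and on deaths being retained. The last is reasonable because 9.1.3 counts all deaths as serious adverse events. A reader might infer a material threat to the primary result; the documents do not support one. Differing practice between sites is a possibility, not something the documents show.

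**What to change.** - **5.6:** replace removal from the study with: *any remaining IP is discontinued; the participant remains in the study under 4.4.2 and all scheduled scores and safety follow-up are collected*.
- **5.2.3:** make the same change to the withdrawal of mTOR inhibitor users, keeping the standard-of-care and hold conditions.
- **8.2:** add that participants who stop IP without withdrawing consent contribute their observed Day 14 score.

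The cost is two edited sentences and one added clause. The scores and safety follow-up are already scheduled, and the sample size, visits and interaction rules do not change. Section 4.4.4 and Appendix 2 can stand as they are. In particular, a footnote making failure of any eligibility criterion at Days 8-9 stop study drug should be avoided: read literally it could halt dosing in hospitalized participants, for whom 5.4 allows dosing where feasible.

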### 5.7 Packaging

The study medication will be prepared and dispensed by the research or general pharmacy associated with the nursing home with appropriate labeling to include a statement that these products are for investigational use only.

### 5.8 Masking/Blinding of Study

In order to minimize the study bias, this study will use a process for randomized assignment to either active Fisetin or placebo (see Section 5.3). The investigational drug blind will be maintained using the processes of the research or general pharmacy associated with the nursing home for preparation of the investigational product. All subjects and study personnel except for those directly involved with IP preparation will be blinded to IP assignment until the end of the study. All unblinded dosing information must be maintained in a secured area, accessible only by unblinded personnel.

# 5.9. Unmasking/ Unblinding Procedure

The investigational drug blind shall not be broken by the investigator unless information concerning the investigational drug is necessary for the medical treatment of the subject. In the event of a medical emergency, if possible, the sponsor-investigator or PI should be contacted before the investigational drug blind is broken to discuss the need for unblinding.

If the PI or patient's attending physician, nurse-practitioner, or physician's assistant decides emergency unblinding is medically necessary, the PI or patient's attending physician, nurse-practitioner, or physician's assistant needs to contact the research or general pharmacy associated with the nursing home. The sponsor-investigator must be notified as soon as possible if the investigational drug blind is broken. The date, time, and reason the blind is broken must be recorded in the source documents, CRFs, or Event forms/logs.

# 5.10 Receiving, Storage, Dispensing, and Return

### 5.10.1. Receipt of IP

The IP for this study will be delivered to and managed by the research or general pharmacy associated with the nursing home according to their established standard procedures.

### 5.10.2. Storage of IP

IP should be stored between the temperatures of 2-30 degrees C.

### 5.10.3. Dispensing of IP

The IP is to be used exclusively in the clinical study according to the instructions of this protocol and directions for use. The Principal Investigator's designee is responsible for providing nursing home staff caring for the subjects with the IP and instructions for dosing and proper storage of the IP. The Principal Investigator's designee will record the amount of IP dispensed, date of dispensing, as well as the amount of IP returned and IP remaining.

#### 5.10.4. Return or Destruction of IP

At the completion of the study, there will be a final reconciliation of IP shipped, IP dispensed, IP returned, and IP remaining. This reconciliation will be logged on the IP reconciliation form, signed, and dated. Any discrepancies noted will be documented and investigated, prior to return or destruction of unused IP. IP destroyed on site will be documented in the study files.

# **6** Study Procedures

The study procedures to be conducted for each subject enrolled in the study are presented in tabular form in Appendix 2 and described in the text that follows.

STUDY STAFF WILL HAVE DIRECT CONTACT WITH STUDY SUBJECTS; STUDY STAFF WILL OBTAIN A MAJORITY OF THE DATA FOR THIS STUDY BY COMMUNICATING WITH NURSING HOME STAFF AND ABSTRACTING INFORMATION FROM THE SUBJECT'S NURSING HOME CHARTS.

For each nursing home, during discussions leading to participation with their administrators and medical and nursing leadership, a key contact will be identified who will ensure access, data and sample collection, and data integrity and identify and assist in resolving issues as the study proceeds. In most cases, this will be the Medical or Nursing Director or their designees.

Biosafety Level 2 (BSL2) containment practices will be followed for sample transport.

# 6.1 Screening Visit (Days -2 to 0)

Patients will be pre-screened prior to being recruited for the study. Subjects will be screened within 3 days before randomization to determine eligibility for participation in the study.

Written informed consent will be obtained from the nursing home resident or from a Legally Authorized Representative (LAR) who can provide informed consent. Sections B to E (B: Hearing, Speech, and Vision, C: Cognitive Patterns, including the Brief Interview for Mental Status, D: Mood, and E: Behavior) of the most recent (within the last 100 days) Minimum Data Set (MDS) will be utilized to determine participants' ability to provide a truly informed consent and such an ability should be verified by staff with access to the nursing homes (e.g., Medical or Nursing Director, nurse practitioner, physician's assistant) and if the participant is not able, their LAR will be asked. All MDS datasets for each subject will be collected throughout their inclusion in the study (up to 194 days) and the date(s) and type of vaccinations for CoV will be recorded.

In the pandemic situation where access to nursing homes and hospitals is limited, if allowed, digital/electronic consent will be obtained from the patient's LAR and will be documented by the investigator or the authorized designee. For any subject, it is the responsibility of the investigator or study team member to obtain consent prior to performing any protocol-mandated assessment.

After the informed consent and agreement by the patient's nursing home attending physician, nurse-practitioner, or physician's assistant, the following assessments are performed to determine eligibility requirements as specified in the inclusion and exclusion criteria. Assessments performed as part of the routine care of the subject by nursing home staff may be used to assess eligibility.

- Demographics.
- Focused medical history including the following information if feasible: date of first symptoms, overall symptoms, exposure source, demographics, baseline characteristics, allergies, medical history, reasons for nursing home admission (diagnoses, key symptoms and signs at and since admission as abstracted from the most recent MDS or available nursing home records).
- Determination of Ordinal Scale score.
- Review of concomitant medications including any COVID-19 vaccinations.
- Review of adverse events.
- Vital signs heart rate, temperature, blood pressure, body weight, oxygenation (use of supplemental oxygen, amount of supplemental oxygen and Sp02 (if possible)) and

- respiratory rate. Preferably, height will be obtained during the Screening visit (but may be obtained at a later visit, if it cannot be obtained during the Screening visit).
- SARS-CoV-2 mRNA-PCR/Influenza & RSV Rapid Test (during the influenza season) in a Mayo Clinic or other CLIA certified laboratory prior to randomization.
- Safety Labs must be collected and assessed within 48 hours prior to randomization. These labs include: bilirubin, creatinine, AST, ALT, hemoglobin, white blood cells, platelet count, absolute neutrophil count, lymphocyte count, plasma or serum glucose, and eGFR.
- If clinical chest imaging (X-ray, CT, MRI) is performed during the subject's participation in the study or within 14 days prior to enrollment, results may be obtained.
- Record any SAEs and all AEs related to protocol-mandated procedures occurring after completion of the consent form.

Subjects who qualify should be immediately randomized. Randomization and dosing should occur on the same day if possible.

# 6.2 Baseline (Day 0 & Day 1) – IP Administration

The following evaluations are to be completed at the screening or Day 0 visit. The investigator must have confirmed eligibility before proceeding with randomization on the Day 0 visit. Participants should complete the following assessments before being administered IP if feasible.

Patients who meet eligibility criteria, including a positive SARS-CoV-2 PCR and, during the influenza season, a rapid influenza and RSV test at a Mayo Clinic or other CLIA certified laboratory before randomization, and do not have evidence of unstable (as *per* clinical judgment) anemia, diabetes, liver disease, or renal dysfunction:

- Eligibility confirmation.
- Determination of Ordinal Scale score.
- Review of concomitant medications.
- Review of adverse events.
- Vital signs heart rate, temperature, blood pressure, body weight, oxygenation (use of supplemental oxygen, amount of supplement oxygen used and Sp02 (if possible)) and respiratory rate. Collection of most recent (at least within 100 or fewer days) Minimal Data Set (MDS) on record for that participant).
- If clinical chest imaging (X-ray, CT, MRI) is performed during the subject's participation in the study or within 14 days prior to enrollment, results may be obtained.
- The 1st IP administration will occur on Day 0. The 2nd IP administration will occur on Day 1 (12 to 36 hours after the 1st IP administration).

# 6.3 Day 8 & Day 9 – IP Administration

- Verify eligibility to re-dose.
- Determination of Ordinal Scale score.
- Review of concomitant medications.
- Review of adverse events.
- Vital signs heart rate, temperature, blood pressure, body weight, oxygenation (use of supplemental oxygen, amount of supplement oxygen used and Sp02 (if possible)) and respiratory rate. If clinical chest imaging (X-ray, CT, MRI) is performed during the subject's participation in the study, results may be obtained.
- The 3rd IP administration will occur on Day 8. The 4th IP administration will occur on Day 9 (12 to 36 hours after the 3rd IP administration).

